7.7.3. Adverse Event Documentation

All adverse events must be fully recorded on the Adverse Event Page via the Electronic Data Capture (EDC) system. Documentation must be supported by an entry in the subject file. Laboratory test, vital signs and ECG abnormalities considered by the Investigator to be clinically relevant should be reported on the Adverse Event page of the eCRF. Signs and symptoms of each AE should be described in detail (e.g., start and stop dates, severity/intensity, relationship to investigational product, action taken, and outcome).

Adverse events and laboratory test abnormalities fulfilling the definition of a serious adverse event should, in addition, be reported on the Serious Adverse Event Reporting Form.

7.7.4. Reporting of Serious Adverse Events

Study site personnel must alert Eli Lilly or its designee of any SAE within 24 hours of their awareness of the event via a sponsor-approved method. Alerts issued via telephone are to be immediately followed with official notification on study-specific SAE forms.

Serious adverse events occurring after a subject receive a dose of investigational product will be collected until 48 hours after the dosing of the investigational product, regardless of the investigator's opinion of causation. Therefore, SAEs that occur later than 48 hours after the dosing of the investigational product are not required to be reported unless the investigator feels the events were related to either investigational product or a protocol procedure.

If a patient experiences an SAE after signing informed consent, but prior to receiving investigational product, the event will NOT be reported unless the investigator feels the event may have been caused by a protocol procedure. Previously planned (prior to signing the ICF) surgeries should not be reported as SAEs unless the underlying medical condition has worsened during the course of the study.

8. STATISTICAL ANALYSIS

8.1. General Statistical Considerations

All statistical analyses will be performed using SAS® version 8.2 or higher.

Data will be summarized using descriptive statistics (number of subjects [N], mean, standard deviation [SD], median, quartiles, minimum, and maximum) for continuous variables and using frequency count and percentage for discrete variables. The demographic and baseline characteristics data will be summarized according to clinical

group (healthy volunteers and subjects with cognitive impairment) at recruitment for all subjects in the safety population. Safety data will be summarized for all patients.

Subject listings of all data from the electronic case report forms (eCRFs) as well as any derived variables will be presented.

Additional details concerning statistical analyses will be included in the Statistical Analysis Plan (SAP).

8.1.1. Sample Size Estimation

8.1.1.1. Exploratory Phase

A total of 230 subjects (80 cognitively healthy volunteers, 80 MCI and 70 AD) will be enrolled in the Exploratory Phase study. To explore the ¹⁸F-AV-1451 SUVR values across age strata among cognitively healthy subjects, these subjects will be divided into 5 age groups as 20-40 years old, 50-59 years old, 60-69 years old, 70-79 years old and 80 years old or above. There will be 15 subjects in each of the 50 or older age groups and about 20 subjects from age group 20-40 years old. From a preliminary analysis of study T807000, the standard deviation (SD) of SUVR from combination ROI was 0.06 for subjects with low probability of AD. Therefore assuming a 0.06 SD, a sample of 15 subjects will give an approximately 90% probability to observe a 95% confidence interval (CI) as accurate as +/-0.04 around the point estimation.

From previous studies, the amyloid positive rate is approximately 50% among MCI patients and approximately 80% from AD subjects. Therefore 80 MCIs and 70 ADs will likely result in 40 amyloid positive MCIs and 56 amyloid positive ADs. Also from study T807000, the combination ROI SUVR difference between CN and AD was 0.39, with a pooled SD of 0.27. Assume a pooled SD of 0.30, a sample of 60 CNs and 56 amyloid positive ADs will give a 90% power to detect a 0.18 difference between the CN and AD groups.

8.1.1.2. Confirmatory Phase

The final hypothesis and endpoint measurements for the Confirmatory Phase are yet to be determined and will depend on the discoveries from Exploratory Phase data. However the primary objective of the confirmatory phase is to validate the accuracy of ¹⁸F-AV-1451 scans to predict clinically significant disease progression within 18 months from scan (e.g., cognitive function deterioration as measured by endpoints based on Exploratory Phase results). For the purpose of sample size calculation, we assumed that the target success criteria would be at least 70% sensitivity and at least 70% specificity for ¹⁸F-AV-1451 scans to detect this deterioration, with the lower bound of 95% confidence intervals (CI) above 50% for both sensitivity and specificity. Preliminary analysis of the exploratory phase cohort data showed that clinical assessments may have a relatively large variance. It is important to ensure that enough subjects will be in each group for sensitivity and specificity calculation (i.e., the subjects with or without a significant disease progression). To that end, we assume at least 20% of the subjects will be in each group at the 18 month follow up. With this assumption, a 5% two-sided type I error rate,

and that 95% CI will be calculated using Wilson score method, a sample of 115 subjects will provide an over 90% probability to observe lower bound of 95% CI above 50%, for both sensitivity and specificity. Also assuming an approximate 20% drop out rate over the 18 months follow up, this study will aim to enroll 150 subjects in total.

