7. Ability to provide informed consent for study procedures (If the patient is ineligible to give informed consent, based on local standards, the patient's legal representative may consent on behalf of the patient but the patient must still confirm assent. This person may serve as the study partner as well).

Subjects who meet all of the following criteria are eligible to enroll in the second phase of this trial: Confirmatory Cohort:

1. Male or female subjects ≥ 50 years of age (n = approximately 150)

2. Cognitively impaired subjects (MCI or dementia with a suspected neurodegenerative cause) with an MMSE ≥ 20 and ≤ 27 . (For the purpose of ensuring a distribution of disease severity, a target of at least 1/3 of the enrolled subjects will have dementia).
3. Have a study partner who has significant interaction with the subject and can report on the subject's activities of daily living
4. Can tolerate PET imaging procedures
5. Can tolerate MRI scan procedures, and
6. Ability to provide informed consent for study procedures (If the patient is ineligible to give informed consent, based on local standards, the patient's legal representative may consent on behalf of the patient but the patient must still confirm assent. This person may serve as the study partner as well).

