8.6.2.4.3 Association of CDR Global Change at 18 Months with Tau Status

The association of change in CDR global score at 18 months by tau status (AD++ vs. non-AD++) will be assessed using a Cochran-Armitage trend test. The analysis will be performed with MCI/AD subjects. Frequency table, along with p-values for the trend test will be provided.

8.6.2.4.4 Diagnostic Performance of Baseline Tau Status in Predicting Clinical Meaningful Changes at 18 Months

This analyses will be restricted to AD/MCI subjects only.

For each cognitive assessment of cognitive impairment and TAU status, a 2x2 table will be generated and the appropriated diagnostic performance parameters determined.

CMC+ is defined as the clinically meaningful changes assessed by psychometric scores are defined in section 6.4.2.3.1. CMC- are those patient with related data but not meet the CMC+ definition.

		Clinical meaningful changes	
		CMC+	CMC-
AD++	A	B	
Non-AD++	C	D	

Sensitivity is defined as the number of Tau+ subjects who are cognitively impaired divided by the total number of subject with cognitive impairment.: $A/(A+C)$

Specificity is defined as the number of Tau- subjects who are not cognitively impaired divided by the total number of subjects without cognitive impairment. : $D/(B+D)$

Accuracy is defined as the number of subjects with cognitive impairment who are Tau+ and the number of subjects without cognitive impairment who are Tau- divided by the total number of patients. : $(A+D)/(A+B+C+D)$

Positive predictive Value is defined as the number of Tau+ subjects who are cognitively impaired divided by the total number of subjects who tested Tau+: $A/(A+B)$

Negative predictive value is defined as the number of Tau- subjects who are cognitively not impaired divided by the total number of subjects who test Tau-: $D/(C+D)$

Positive Likelihood Ratio (LR+) for positive result shows the odds of the cognitive impairment increases when TAU+: $Sensitivity/(1-Specificity)$

Negative Likelihood Ratio (LR-) for negative result shows the odds of the cognitive impairment decreases when TAU- : $(1-Sensitivity)/Specificity$

Relative risk: $(A/(A+B))/(C/(C+D))$

The analyses from 8.6.4.2.1 – 8.6.2.4.2, and 8.6.2.4.4 will be repeated with subjects with AD/MCI diagnosis and baseline MMSE 20 -27, which is similar to the target enrolled population in confirmatory cohort.

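### Accuracy tables and tau-status models pool MCI with AD and leave out baseline diagnosis, so part of any scan–progression association may be diagnosis, and no document commits to separating them

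*Protocol*

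**What the plan says.** **Confirmatory phase.** Protocol 5.3.1 admits MCI and dementia together (MMSE 20 to 27), with "a target of at least 1/3 of the enrolled subjects will have dementia" and no upper limit. For sample size, Protocol 8.1.1.2 supposes that the "target success criteria would be at least 70% sensitivity and at least 70% specificity", "with the lower bound of 95% confidence intervals (CI) above 50% for both sensitivity and specificity". The bound is a fixed number; no other predictor is set beside the scan. Sections 8.1.1.2 and 8.1.4 leave the final hypothesis open and defer the analysis to a later SAP. They name MMRM, risk-ratio and time-to-event analyses as possibilities, without a diagnosis stratum, covariate or comparator.

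**Exploratory phase.** The SAP supplied covers this phase only (SAP 3). Section 8.6.2.4.4 cross-classifies baseline tau read (AD++ or not) against clinically meaningful change and says: "This analyses will be restricted to AD/MCI subjects only". It gives one pooled table per outcome. The MMRM and CDR-SB ANCOVA (8.6.2.4.1) and the Poisson model (8.6.2.4.2) adjust for baseline psychometric score, age and ANART. Diagnosis is in none of them, although the title of 8.6.2.4.1 refers to diagnostic groups.

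**The concern.** The trial's primary cross-sectional objective is to compare uptake between AD, MCI and healthy older subjects, so the scan is expected to differ by diagnosis. If dementia also progresses faster than MCI, diagnosis confounds the association between scan and progression. A pooled table credits the scan with whatever it shares with diagnosis, which the clinician has already recorded at enrolment.

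Two features add to this. The SAP says amyloid readers are blinded to diagnostic group (6.4.2.1) but says no such thing for the exploratory tau reads, which the sponsor's own experts make (6.4.1.2). And exploratory results are to generate the confirmatory hypothesis (Protocol 8.1.4), so an association that is partly diagnosis would carry forward into the choice of endpoint and read rule.

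**Working it through.** **1. The plan's own figure.** Protocol 8.1.1.2 says that "a sample of 115 subjects will provide an over 90% probability to observe lower bound of 95% CI above 50"%, for both measures. Its inputs are: "we assume at least 20% of the subjects will be in each group at the 18 month follow up"; "a 5% two-sided type I error rate"; and "95% CI will be calculated using Wilson score method". With 23 and 92 subjects in the two outcome groups, the Wilson bound passes 50% at 17/23 and 56/92 correct. At true accuracy of 70%/70% the chance is 0.44 × 0.98 = 43%. It exceeds 90% only at about 83% true accuracy (92%), which the protocol does not state. That is a separate matter; here only the bar itself is used.

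**2. Diagnosis as the test.** Let f be the dementia share, and a and b the 18-month progression rates in dementia and MCI.

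- sensitivity = f·a / [f·a + (1−f)·b]
- specificity = (1−f)(1−b) / [(1−f)(1−b) + f(1−a)]
- Wilson lower bound = [p + z²/2n − z√(p(1−p)/n + z²/4n²)] / (1 + z²/n), with z = 1.96 and n the expected number of progressors (or non-progressors) among 115

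The documents give no rates by diagnosis. I assume a = 50, 60 or 70% and b = 20 or 25%. Example at f = 0.5, a = 50%, b = 25%: progressors 115 × 0.375 = 43.1; sensitivity 0.25/0.375 = 66.7%; specificity 0.375/0.625 = 60.0%; bounds 51.8% and 48.4%, a fail.

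Cells show sensitivity/specificity (lower bounds), in percent.

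| a / b | one third dementia | 40% dementia | half dementia |
|---|---|---|---|
| 50/20 | 55.6/76.2 (39.3, 65.8) fail | 62.5/70.6 (46.4, 59.7) fail | 71.4/61.5 (56.1, 50.2) pass |
| 50/25 | 50.0/75.0 (34.9, 64.3) fail | 57.1/69.2 (41.9, 58.0) fail | 66.7/60.0 (51.8, 48.4) fail |
| 60/20 | 60.0/80.0 (44.3, 69.7) fail | 66.7/75.0 (51.4, 64.0) pass | 75.0/66.7 (60.9, 54.9) pass |
| 60/25 | 54.5/78.9 (39.8, 68.3) fail | 61.5/73.8 (46.9, 62.4) fail | 70.6/65.2 (56.7, 53.2) pass |
| 70/20 | 63.6/84.2 (48.6, 74.2) fail | 70.0/80.0 (55.6, 69.1) pass | 77.8/72.7 (64.8, 60.7) pass |
| 70/25 | 58.3/83.3 (44.0, 72.8) fail | 65.1/78.9 (51.2, 67.6) pass | 73.7/71.4 (60.7, 59.0) pass |

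Both bounds pass in 0, 3 and 5 of six cases. The 70%/70% point target is also met at 70/20 with 40% dementia, and at 70/20 and 70/25 with half dementia.

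These are results at expected values. Allowing for sampling, the chance that both bounds pass at 50/20, 60/20 and 70/20 is 41%, 76% and 95% at half dementia, and 9.5%, 23% and 43% at one third.

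For diagnosis to reach 70% sensitivity, a/b must equal (0.7/0.3)(1−f)/f: 4.67 at one third, 3.5 at 40%, 2.33 at half.

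**3. A scan with no information within diagnosis.** Take the exploratory mix of 70 AD and 80 MCI (70/150 = 47% AD). Assume AD++ in 60 or 75% of AD and 20 or 30% of MCI, independent of outcome within each diagnosis, with the same a and b. That gives 24 combinations.

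- Lowest relative risk (a = 50%, b = 25%, AD++ 60%/30%): progressors 35 + 20 = 55. AD++ among them is 35 × 0.6 + 20 × 0.3 = 27, so sensitivity is 27/55 = 49.1%. AD++ among the 95 non-progressors is 35 × 0.6 + 60 × 0.3 = 39, so specificity is 56/95 = 58.9%. Relative risk (27/66)/(28/84) = 1.23.
- Highest (a = 70%, b = 20%, AD++ 75%/20%): sensitivity 39.95/65 = 61.5%; specificity 1 − 28.55/85 = 66.4%; relative risk (39.95/68.5)/(25.05/81.5) = 1.90.

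Over all 24: sensitivity 45–64%, specificity 53–70%, relative risk 1.2–1.9, where the within-diagnosis relative risk is exactly 1. Repeating the grid at one third and half dementia (n = 115) makes 72 combinations. In none do both lower bounds exceed 50%.

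**The case against.** The case on the other side is substantial.

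- **The aim is accuracy, not added value.** Protocol 2.3 speaks of confirming a relationship and 8.1.1.2 of validating accuracy. This stands: silence on diagnosis does not contradict the stated aim. It does limit what a positive result would mean.
- **The confirmatory analysis is not yet written.** This stands too. A reader might infer that the plan cannot show whether the scan adds to diagnosis. The documents do not support that: the bar is a sample-size assumption, and the later SAP may include such a test. They support only that no commitment has been made.
- **The bar might seem reachable by diagnosis, or by any scan that tracks it.** A reader might infer this too, but it does not hold generally. At the one-third target, diagnosis fails in all six cases, and an imperfect proxy failed in all 72 combinations. Passing needs a larger dementia share or a stronger contrast in progression. The protocol allows a share near half but does not plan one.
- **Severity is already partly handled.** The models include baseline score; the main analyses are repeated at MMSE 20–27; and 8.6.2.4.5 plots change against baseline SUVr by diagnostic group. This is real mitigation. But the accuracy tables carry no adjustment, and the MCI criteria turn on preserved independence and absence of dementia (Protocol 5.3.1), which a cognitive score captures only in part. The plots use SUVr, not the AD++ read that the tables test.

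**Conclusion.** The point holds in a limited form. As planned, the exploratory accuracy tables and tau-status models cannot tell how much of a scan–progression association is diagnosis, and nothing in either document commits the confirmatory phase to doing so. Under the assumed rates, the pooled tables could show a relative risk of 1.2–1.9 for a scan with no information within diagnosis; such a scan looks prognostic but does not reach the success bar. That range applies to the unadjusted tables; the models' adjustment for baseline score would remove some of it, by an amount the documents do not let one compute. Whether diagnosis itself would reach the bar depends on the dementia share and on progression rates that the documents do not give.

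**What to change.** 1. In SAP 8.6.2.4.4, report each 2×2 table within MCI and within AD as well as pooled. Add a row giving the same measures with baseline diagnosis (dementia against MCI) as the test.
2. Alongside the planned MMRM, CDR-SB ANCOVA and Poisson models, fit each once more with baseline diagnosis as a covariate.
3. Carry diagnosis-stratified accuracy and a Mantel–Haenszel odds ratio, stratified by diagnosis, into the confirmatory SAP as supportive analyses, fixed before the data are seen.

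Diagnosis is already recorded, so the cost is extra table rows and one more fit per model. Intervals within diagnosis will be wider, so these results should be read as estimates, not held to the 50% bound.

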8.1.4. Confirmatory Phase

Longitudinal data from the exploratory study phase will be assessed periodically to determine the relationships between various ¹⁸F-AV-1451 imaging parameters (e.g., composite and regional SUV_r, voxel based statistics and visual interpretation) and the change from baseline in the various cognitive and functional assessments. These data will be used to generate hypotheses regarding the relationship between ¹⁸F-AV-1451 PET tau imaging and cognitive/functional change that will be formally incorporated into an analysis plan and tested in the confirmatory stage of the study.

Based on discoveries using data from Exploratory Phase, a disease progression measurement will be chosen as truth standard (TS), and the accuracy of ¹⁸F-AV-1451 PET scans to detect this TS within 18 months of scan will be evaluated. Hypothesis testing and detailed analyses will be described in a statistical analysis plan (SAP), which will be finalized prior to database lock. Possible analyses include calculation of accuracy measures such as sensitivity, specificity, and two sided 95% confidence intervals (CI) around these rates. Other analyses may include Mixed-Effect Model Repeated Measures (MMRM) analysis, risk ratio analysis, and time to event analysis.

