3 STUDY OBJECTIVES

This study will be conducted in two phases, an exploratory phase and a confirmatory phase. This statistical analysis plan is for the exploratory phase of this study. The exploratory phase of this study will be comprised of a cross-sectional component and a longitudinal component.

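### The probability of over 90% given for 115 confirmatory subjects does not follow from the stated inputs: at 70%/70% it is 43% to 79%, and the higher true accuracy it needs is not stated

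*Protocol*

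**What the plan says.** Protocol section 8.1.1.2 sets out the confirmatory calculation. For sizing purposes, "we assumed that the target success criteria would be at least 70% sensitivity and at least 70% specificity", "with the lower bound of 95% confidence intervals (CI) above 50% for both sensitivity and specificity". On the split between subjects with and without progression, "we assume at least 20% of the subjects will be in each group at the 18 month follow up". The error rate is 5% two-sided and the intervals are Wilson score intervals. From these the protocol concludes that "a sample of 115 subjects will provide an over 90% probability to observe lower bound of 95% CI above 50" percent for both measures. It then allows for about 20% dropout and says that "this study will aim to enroll 150 subjects in total".

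The section begins by saying that the final hypothesis and endpoints are still open. Section 8.1.4 adds: "Hypothesis testing and detailed analyses will be described in a statistical analysis plan (SAP), which will be finalized prior to database lock". The SAP supplied cannot be that document, since its section 3 says: "This statistical analysis plan is for the exploratory phase of this study". Its sample-size section (4.5) contains only the exploratory calculation.

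**The concern.** The probability of clearing a 50% lower bound depends on sample size, the split between the two groups, the interval method, and the true sensitivity and specificity. The protocol gives all of these except the last. The only accuracy it mentions is 70%, adopted expressly for the sample size calculation, so a reader will naturally put 70% into the calculation. The result is then well short of 90%.

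In the documents supplied, this is the only probability offered in support of 115 evaluable and 150 enrolled confirmatory subjects. Anyone who takes 70% as the design accuracy will overstate the chance of meeting the interval criterion by about 11 to 47 percentage points (90 − 78.8 to 90 − 43.0), depending on the split. The phase is meant to validate independently what the exploratory phase found, so its planned chance of success should be open to checking.

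**Working it through.** **Inputs, all from Protocol section 8.1.1.2.** N = 115 evaluable; at least 20% in each outcome group, so the smaller group has from 0.20 × 115 = 23 up to 57 subjects; two-sided 95% Wilson interval; both lower bounds above 0.50; accuracy 70% for each measure, the only value given.

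**Method.** With observed proportion p̂ = x/n and z = 1.96, the Wilson lower bound is

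[p̂ + z²/(2n) − z√(p̂(1−p̂)/n + z²/(4n²))] / (1 + z²/n).

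For each group size, find the smallest count r whose bound exceeds 0.50, then compute P(X ≥ r) for X ~ Binomial(n, true accuracy). Sensitivity and specificity come from different subjects, so the joint probability is the product of the two.

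**Attempt to reproduce the plan's figure at 70%/70%.**

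- Floor, 23/92. 16/23 gives a bound of 0.491 and 17/23 gives 0.535, so r = 17 and P = 0.440. For n = 92, r = 56 and P = 0.977. Joint: 0.440 × 0.977 = 0.430.
- One subject more in the smaller group, 24/91. r = 17 (bound 0.508), P = 0.565; r = 55, P = 0.980. Joint: 0.554.
- Even split, 57/58. r = 36 and 37, P = 0.897 and 0.879. Joint: 0.788.

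Over every split with at least 23 in each group, the minimum is 0.430 and the maximum 0.788. The figure of over 90% is not reproduced.

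**Other readings tried at 70%/70% with 115 subjects.** A one-sided 95% bound gives 0.56 to 0.87. Continuity-corrected Wilson gives 0.43 to 0.74 at the splits tried. Treating the group sizes as random, with 20% to 50% progressing, gives 0.49 to 0.76. A value above 0.90 appears only for the larger group alone (0.977 at n = 92) or if just one of the two measures had to succeed (0.987). The text requires both.

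**Dropout allowance.** 115/0.8 = 143.75 and 150 × 0.8 = 120, so enrolling 150 is consistent with 115 evaluable. The extra five subjects do not close the gap: at 70%/70%, 120 subjects give 0.555 at 24/96 and 0.803 at 60/60.

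**What true accuracy would support the statement.** Joint probability with N = 115 and equal true sensitivity and specificity:

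| Split | 70% | 75% | 80% | 85% | Smallest accuracy giving over 0.90 |
|---|---|---|---|---|---|
| 23/92 (floor) | 0.430 | 0.653 | 0.840 | 0.954 | 0.822 |
| 24/91 | 0.554 | 0.766 | 0.911 | 0.980 | 0.796 |
| 34/81 | 0.663 | 0.878 | 0.973 | 0.997 | 0.758 |
| 46/69 | 0.755 | 0.945 | 0.994 | >0.999 | 0.733 |
| 57/58 | 0.788 | 0.964 | 0.998 | >0.999 | 0.725 |

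**If 70% is a pass mark for the observed rates.** Success then needs both an observed rate of at least 70% and a lower bound above 50%, for each measure. The critical counts become the larger of the Wilson count and 0.70n rounded up: at 23/92 these are 17 and 65, giving 0.219 at true 70%. Across permitted splits the probability of meeting both halves is 0.22 to 0.30 at true 70%, 0.56 to 0.69 at 75%, and 0.83 to 0.94 at 80%.

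**The case against.** The strongest reply is that the protocol never says the true accuracy is 70%. It says "the target success criteria would be at least 70% sensitivity and at least 70% specificity", which is an inequality worded as a criterion, and planning at a true value above the pass mark is ordinary practice. On that reading no stated inputs have been shown to give a wrong output; one input is missing. The figure is also attainable at a plausible accuracy: at true 80%/80% the joint probability exceeds 0.90 at every permitted split except 23/92 (0.840) and 25/90 (0.891), and with 120 evaluable subjects the floor split of 24/96 gives 0.911. The 43% figure is a low point of the discrete binomial at a boundary split. Finally, the section is openly provisional, and a confirmatory SAP that may contain the assumption is not among the documents supplied.

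Much of this is fair. A design value near 80% may lie behind the figure, and 23/92 should not be read as the expected case. But the reply concedes the defect, because the assumption that drives the answer is not written down. The conclusion does not rest on the floor case, since no permitted split reaches 0.79 at 70%. The pass-mark reading brings its own difficulty: the stated probability then covers only the interval half of the criterion. And although the hypothesis is provisional, the protocol still commits to a specific number of subjects and a specific probability.

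**Conclusion.** The statement is wrong as written: the stated inputs do not yield a probability above 90%. With 115 subjects and 70%/70%, the joint probability is 0.430 to 0.788 across permitted splits. Exceeding 0.90 requires an unstated true accuracy of 72.5% to 82.2%, depending on the split. These figures assume equal true sensitivity and specificity, fixed group sizes, independence between subjects, and two-sided 95% Wilson bounds. They do not show that 115 or 150 is the wrong number, only that its stated justification cannot be obtained from what is written. Because this is the sole probability supporting the confirmatory cohort, it should be corrected before the protocol and confirmatory SAP are relied on.

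**What to change.** In Protocol section 8.1.1.2 and in the confirmatory SAP:

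1. State the assumed true sensitivity and specificity, separately from the success criterion.
2. Say whether 70% is a pass mark for the observed rates or a design value. If it is a pass mark, give the probability of meeting both halves of the criterion.
3. Replace the single probability with a short table of joint probability by true accuracy (70%, 75%, 80%, 85%) and split (23/92, 24/91, 34/81, 46/69, 57/58), with 23/92 marked as the 20% floor. The table above can serve for the interval half.

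This costs one paragraph and one small table. It adds no subjects and leaves the analysis unchanged. The price is a less favourable stated probability where true accuracy is low.
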